14.3 Patient Disposition and Characteristics

Demography and other baseline characteristics will be summarized descriptively for both the FAS and Safety population (if different), overall and by treatment group. Demography and other baseline characteristics will be summarized descriptively overall and by treatment group as well as by subgroup (sprains/strains, contusions). For quantitative data, means, medians, standard deviations and extremes will be determined. For qualitative data, absolute and relative frequencies will be calculated. Important baseline characteristics will be further summarized by sex, race and age.

14.4 Efficacy

14.4.1 Primary efficacy variable

Change from baseline in pain-on-movement (POM) at injured site in mm measured using a 100 mm Visual Analogue Scale (VAS) to Visit 5 (72 hours after commencement of study treatment)

The analysis of the primary endpoint will be adjusted for baseline values. The baseline adjusted difference between active treatment and placebo at 72 hours should be > 10 mm. Magnitude of reduction in pain will be used to determine 'responder rate'.

For the primary variable an analysis-of-covariance (ANCOVA) with baseline as covariate and treatment, center and subgroup as factors will be carried out. A closed testing procedure controlling the multiple α -level of 5 % will be used in the analysis:

1) H₀: $\mu_E=\mu_P$ vs. H₁: $\mu_E\neq\mu_P$. In case of a significant result for this first hypothesis two further hypotheses regarding the subgroups "sprains/strains" and "contusions" will be then be also tested by means of the same baseline adjusted ANCOVA model to the 5 % level. In case of significance, the following subhypotheses are simultaneously tested at the 5 % level of significance.

2a) H₀: $\mu_E(\text{spr/str})=\mu_P(\text{spr/str})$ vs. H₁: $\mu_E(\text{spr/str})\neq\mu_P(\text{spr/str})$ in the subgroup "Sprains/strains",

2b) H₀: $\mu_E(con) = \mu_P(con)$ vs. H₁: $\mu_E(con) \neq \mu_P(con)$ in the subgroup "contusions".

CRMB	Trial Substance:	Esflurbiprofen Hydrogel Patch	Study No.: TK-254R-0201 EudraCT No.: 2020-005165-14
	Short Title:	Local symptomatic and short-term treatment of pain in acute strains, sprains or bruises of the extremities following blunt trauma	Sponsor: TEIKOKU SEIYAKU CO LTD.

The primary analysis population is the Full Analysis Set (FAS).

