5.1 Inclusion criteria

Patients eligible for inclusion in this study must fulfill all of the following criteria: The following must apply:

- 1. acute sports-related soft-tissue injury/contusion (strains, sprains, bruises) of the upper or lower limb
- 2. location of injury such that pain-on-movement (POM) is elicited on by the exercises described in Section 7.5
- 3. enrollment within 6 hours of the injury
- 4. baseline VAS score for POM of injured extremity \geq 50 mm on a 100 mm VAS
- 5. size of injury, as assessed by investigator, $\geq 25 \text{ cm}^2$ and $\leq 120 \text{ cm}^2$
- 6. adult male or female patients
- 7. age 18 to 60 years
- 8. having given written informed consent
- 9. satisfactory health as determined by the Investigator based on medical history and physical examination.

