7.3 Assessment of injury

The size of injury is measured by the Investigator. The size must be at least 25 cm² and at most 120 cm^2 on the basis of the largest perpendicular diameters. The localization should also be documented in detail in the patient CRF.

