7.5 Efficacy

7.5.1 Clinic visit efficacy assessments

The following chronological sequence will be observed for the efficacy assessments below:

- 1. Pain at rest/spontaneous pain (PAR)
- 2. Pain-on-movement (POM)

The global assessments may be completed at any time during the assessment process.

Pain-at-rest (PAR)

PAR will be measured at injured site in mm using a 100 mm VAS at Visits 1-7

The patient will then answer the question:

"How would you describe the pain in the injured area at rest?"

The patient will draw a perpendicular line on a 100 mm Visual Analogue Scale (VAS) with a pen between 0 = "no pain" and 100 = "Extreme pain" to reflect the pain intensity at rest.

|-----|

No pain

Extreme Pain

Pain-on-movement (POM)

POM will be assessed at the study center at Visits 1–7 using a 100 mm VAS. The result will be written in the CRF.

To standardize the procedure for the assessment of pain-on-movement a special movement should be performed by the patient, either for the upper limb or the lower limb depending on which limb is injured.

□ To assess pain-on-movement of the upper limb, the patient will be instructed to grab a 3 kg bar with the hand of the injured arm, slowly lift the bar by bowing the elbow from the 0 position to a 160 degree position and then slowly move the arm back to the starting position.

Figure 7.5.1: Exercise to assess pain-on-movement of the upper limbs

The patient will then answer the question:

"How would you describe the pain in the injured area while you were moving your arm?"

□ To assess the pain-on-movement of the lower limb, the patient will be instructed to slowly walk 5 steps on an even surface. The patient must initiate the walk with the injured limb (i.e. take 3 of the 5 steps with the injured limb).

The patient will then answer the question:

"How would you describe the pain in the injured area while you were walking?"

The patient will draw a perpendicular line on a 100 mm Visual Analogue Scale (VAS) with a pen between 0 = "no pain" and 100 = "Extreme pain" to reflect the pain intensity during movement.

|-----|

No pain

Extreme Pain

Global efficacy assessments

The global efficacy assessments are evaluated by the patient at Visits 4, 5 and 7 as the response to following questions:

- □ "Considering all the ways this treatment has affected you since you started in the study, how well are you doing?" It is assessed on the following 5-point Likert scale:
- 0 = very good
- 1 = good
- 2 = fair
- 3 = poor

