5.3 Other variables

The following other variables are documented in this clinical trial:

- Demographics and other baseline characteristics (documented at Visit 1; age, sex, height, weight, race, ethnicity, localization of injury).
- Check of contraception (at Visit 1).
- Medical history (at Visit 1).
- Concomitant medication (every visit).

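### Pain on movement is measured with different exercises for arm and leg injuries, but injured limb is not in the primary ANCOVA: a possible small loss of precision, not a bias

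*SAP*

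**What the plan says.** Protocol 5.1 admits patients with "acute sports-related soft-tissue injury/contusion (strains, sprains, bruises) of the upper or lower limb". Under Protocol 7.5.1 the POM exercise is chosen "either for the upper limb or the lower limb depending on which limb is injured". An arm patient must "grab a 3 kg bar with the hand of the injured arm" and bend and straighten the elbow. A leg patient must "slowly walk 5 steps on an even surface". The question that follows also differs: one asks about moving the arm, the other about walking. Both answers go on the same 100 mm VAS.

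The primary model is given in the protocol Synopsis, Protocol 9.7.2 and SAP 14.4.1: baseline POM as covariate, with "treatment, center and subgroup as factors will be carried out". Subgroup separates sprains/strains from contusions. Protocol 6.3 stratifies the randomization list by center and the same subgroup, not by limb.

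Limb is available. Protocol 7.3 says "The localization should also be documented in detail in the patient CRF", and SAP 5.3 lists "localization of injury" among the Visit 1 baseline characteristics. SAP 14.4.2 plans further summaries of the primary outcome by sex, age and race, and by center if there is evidence of an interaction. Limb is not on that list.

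**The concern.** A loaded elbow bend and weight-bearing steps are different provocations, and pain on them could recede at different speeds over 72 hours. Baseline POM adjusts for where the patient starts on his or her own exercise. It does not adjust for a different average recovery on that exercise. If such a difference exists, it sits in the residual variance, and a chance imbalance of limb between arms adds noise to the estimate.

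Precision is at stake, most of all in hypotheses 2a and 2b, which are tested on parts of the sample. SAP section 6 says that the size was raised to 90 per group to power those comparisons as well. In addition, no planned summary of the primary outcome would show whether the result looks alike on the two exercises.

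**Working it through.** **Inputs from the documents** (Protocol 9.9, SAP section 6): two-sided 5% t-test, difference 10 mm, SD 20 mm, 64 per group for about 80% power, 90 per group planned, 1:1 allocation.

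**Assumptions, because the documents are silent:**
- Limb split: p = 0.30 in one limb and 0.70 in the other.
- D, the difference between limbs in mean 72 h change given baseline POM, center and subgroup: 0 to 15 mm.
- 20 mm is the residual SD of the planned ANCOVA. The SAP gives it for a t-test and does not say whether it is adjusted.
- 45 per arm in each subgroup, that is, an equal split of 90.

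**Step 1: the plan's own figure.** The normal approximation gives 63 per group. The noncentral t gives 64 per group with power 80.1%, so the stated 64 reproduces. At 90 per group the standard error is 20 × √(2/90) = 2.98 mm and power is 91.6%. At 45 per arm it is 20 × √(2/45) = 4.22 mm and power is 65.0%.

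**Step 2: add limb.** Residual variance becomes 400 − p(1−p)D², and one degree of freedom is spent. For D = 10 mm this is 400 − 0.21 × 100 = 379, so the SD is 19.47 mm. The standard error ratio is 19.47/20 = 0.973, a fall of 2.7%.

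| D (mm) | Variance explained | Residual SD (mm) | Fall in SE | Power, 90 per arm | Power, 45 per arm |
|---|---|---|---|---|---|
| 0 | 0% | 20.00 | 0% | 91.6% | 65.0% |
| 5 | 1.3% | 19.87 | 0.7% | 91.9% | 65.6% |
| 10 | 5.25% | 19.47 | 2.7% | 92.9% | 67.4% |
| 15 | 11.8% | 18.78 | 6.1% | 94.4% | 70.5% |

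The split matters little. For D = 10 mm, power at 90 per arm runs from 92.1% (10:90) to 93.1% (50:50), and at 45 per arm from 66.0% to 67.8%.

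**Step 3: chance imbalance in one trial.** The limb share differs between arms with standard error √(2 × 0.21/n). At n = 45 this is 0.097, a 95% range of about ±19 percentage points. If D = 10 mm, that moves the estimate by up to about ±1.9 mm. At n = 90 the range is about ±13 points, or ±1.3 mm. This is part of the ordinary sampling error, and the table already counts it through the residual SD.

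**Step 4: validity.** ANCOVA was simulated with and without limb (180 patients, 50:50 limbs, D from 0 to 20 mm, 4,000 trials per scenario). Mean estimates lay within about 0.1 mm of the true value in both models. Type I error was 4.4% to 5.9% (Monte Carlo standard error about 0.35 points). The two models differed by at most 0.6 points on the same simulated trials, and the highest rate occurred with limb in the model.

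**The case against.** The strongest case against is that this is a preference and not a defect. Each patient does the same exercise at baseline and at 72 h, treatment is randomized, and the model already contains the baseline outcome and both stratification factors. Nothing in the documents shows that limb is prognostic. The same conditional argument could be made for age, sex or injury size. A 10 mm gap between limbs, as large as the effect the trial is powered for, buys only 1.3 points of power (92.9% − 91.6%). SAP 14.3 summarizes baseline characteristics by treatment group and subgroup, so a limb imbalance should be visible.

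Most of this stands. A reader might infer that pooling two exercises distorts the primary comparison, or that the plan certainly leaves removable variance in the residual. The documents support neither. The comparison is valid without limb, and the loss of precision depends on a gap they do not report. A reader might also infer that chance imbalance goes unaccounted for, but it is reflected in the standard error.

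What does not stand is the parallel with any other covariate. Limb decides which task generates the outcome, so it has a more direct rationale than age or sex. A baseline table would show an imbalance but would not adjust for it.

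**Conclusion.** The point holds as a modest, conditional gain in precision. Limb determines the measuring task, can be derived from a baseline item already collected, and appears in neither the strata nor the primary model. If limb predicts 72 h change given baseline POM, center and subgroup, adding it helps: at 90 per arm by about 0.3, 1.3 or 2.8 power points for conditional gaps of 5, 10 or 15 mm, and at 45 per arm by about 0.6, 2.4 or 5.5 points. If it does not, nothing is gained and one degree of freedom is lost.

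These sizes rest on the assumed 30:70 split, on 20 mm being the residual SD, and on an equal split between the subgroups. Any part of a limb difference that baseline, center or subgroup already absorbs does not count toward the gap. Adding limb would not make up the low power of the subgroup tests: about 70% is reached only with a 15 mm gap.

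**What to change.** Before unblinding, define injured limb (upper/lower) from the Visit 1 localization. Enter it as a fixed factor in the primary ANCOVA, in the models for hypotheses 2a and 2b, and in the other POM models. Report the model without limb as a sensitivity analysis, and add limb to the summaries of the primary outcome in SAP 14.4.2. That section also gives a POM model with treatment, center and baseline but without subgroup, so the model statements should be reconciled in the same edit.

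The cost is one degree of freedom per model and no new data. The timing allows it: SAP section 1 says that the SAP is finalized after the blind review meeting, and the protocol's Data Analysis text has analysis decisions from that meeting documented in the SAP. It is not a SAP-only edit, however. The primary model is also fixed in the protocol Synopsis and Protocol 9.7.2, so the change must be recorded as a departure from that model or made by amendment under Protocol 11.1.

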14.4.2 Secondary efficacy variables

- POM at injured site in mm measured using a 100 mm VAS at 12, 24, 48, 72, 96 and 168 hours after commencement of study treatment and will additionally presented by subgroup (table and Figure).
- AUC over time during first 12, 24, 48, 72, 96 and 168 hours for POM measured using a VAS; ordinate = POM score in mm, abscissa = time after treatment
- Pain-at-rest (PAR) at injured site in mm measured using a 100 mm VAS at 12, 24, 48 72, 96 and 168 hours.
- Reduction in VAS for POM from baseline:
- Time to meaningful reduction (30%)
- Time to optimal reduction (50%)
- Time to complete resolution of pain
- Responder rate 1 (defined as the proportion of patients achieving ≥50% reduction from baseline in the VAS score for POM at 72 hours)
- Responder rate 2 (defined as the proportion of patients able to resume training / normal physical activity by 168 hours)
- Clinical global assessment of efficacy as judged by investigator and patient at 48, 72 and 168 hours
- Overall dose of rescue medication needed (paracetamol).

Statistical test results for secondary variables will only be interpreted exploratorily.

Other important secondary efficacy outcomes are pain-on-movement on VAS at 12, 24, 48, 72, 96 and 168 hours after initiating treatment in the FAS population. These will be analyzed with an analysis-of-covariance (ANCOVA) model and center and subgroup as main effects. All other continuous efficacy outcomes will be analyzed based on the same model (excluding the baseline covariate when there is no appropriate baseline).

Differences between treatments on ordinal outcomes will be tested with Wilcoxon, stratified by center and subgroup.

Figures will show the time course of outcomes by treatment group for key quantitative outcomes. The primary outcome will also be summarized by center (if there is evidence of a treatment-by-center interaction), sex, age and race but without formal statistical comparisons of treatments.

For quantitative outcomes assessed (POM, pain-at-rest) each null hypothesis will be tested with an analysis-on-covariance (ANCOVA) model including treatment group and center as main effects, and the baseline value as covariate (those outcomes for which there is a baseline). The model will be fit both with and without the treatment-by-center interaction. The primary model will be the model without the interaction. If the treatment/center interaction is statistically significant (p<0.05), additional ANCOVAs will be run to identify the center(s) driving the interaction and to lay out the evidence for efficacy among the centers whose results are concordant and centers driving the interaction. ANCOVA outputs will be presented in the Statistical Appendix for the primary and various secondary outcomes to allow an outside reviewer to assess the acceptability of the primary statistical model.

CRMB	Trial Substance:	Esflurbiprofen Hydrogel Patch	Study No.: EudraCT No.:	TK-254R-0201 2020-005165-14
	Short Title:	Local symptomatic and short-term treatment of pain in acute strains, sprains or bruises of the extremities following blunt trauma		KU SEIYAKU CO LTD.

The treatment effects will be estimated as mean differences between the active and placebo groups with 95% confidence intervals.

The response outcome (POM reduced by 50% at Visit 5, Yes/No) will be analyzed by the CMH test of general association, stratified by center and also by subgroup.

Differences between treatments in time-to-event outcomes will be tested with the log-rank test stratified by center.

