5.1.2 Secondary efficacy variables

- POM at injured site in mm measured using a 100 mm VAS at 12, 24, 48, 72, 96 and 168 hours after commencement of study treatment and will additionally presented by subgroups (table and Figure).
- AUC over time during first 12, 24, 48, 72, 96 and 168 hours for POM measured using a VAS; ordinate = POM score in mm, abscissa = time after treatment
- Pain-at-rest (PAR) at injured site in mm measured using a 100 mm VAS at 12, 24, 48 72, 96 and 168 hours.
- Reduction in VAS for POM from baseline:
 - Time to meaningful reduction (30%)
 - \circ Time to optimal reduction (50%)
 - Time to complete resolution of pain
- Responder rate 1 (defined as the proportion of patients achieving ≥50% reduction from baseline in the VAS score for POM at 72 hours)
- Responder rate 2 (defined as the proportion of patients able to resume training / normal physical activity by 168 hours)
- Clinical global assessment of efficacy as judged by investigator and patient at 48, 72 and 168 hours
- Overall dose of rescue medication needed (paracetamol).
- POM on VAS by indication at Visit 5.

Additional outcomes

- Adhesive power of patch (5-point scale)
- Mean adhesion by application site and/or net use.
- If there is significant use of rescue medication, a sensitivity analysis may be performed to assess impact on primary endpoint and responder rate.
- Outcomes will be compared for all use of rescue medication and separately for use to treat blunt trauma. Day 1 and the day of the final visit will count as full days for this purpose. Use of rescue medication on days after study medication has been discontinued will not be counted.
- POM on VAS difference at V4, V5, V6 compared to V1 (BL) (PID V4, PID V5, PID V6) PID V4, PID V5 and PID V6 will be compared between treatment groups using ANCOVA with terms in the model for treatment group, site [as fixed effects], and baseline POM assessment [as a covariate]. Least square mean for each treatment and the

CRMB	Trial Substance:	Esflurbiprofen Hydrogel Patch	Study No.: EudraCT No.:	TK-254R-0201 2020-005165-14
	Short Title:	Local symptomatic and short-term treatment of pain in acute strains, sprains or bruises of the extremities following blunt trauma		OKU SEIYAKU CO LTD.

corresponding difference between least square means with the p-value and 95 % confidence interval will be presented from the specified ANCOVA model.

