14.4.3 Additional exploratory efficacy variables

- •
- Mean adhesion by application site and/or net use.
- If there is significant use of rescue medication, a sensitivity analysis may be performed to assess impact on primary endpoint and responder rate.
- Outcomes will be compared for all use of rescue medication and separately for use to treat blunt trauma. Day 1 and the day of the final visit will count as full days for this purpose. Use of rescue medication on days after study medication has been discontinued will not be counted.
- POM on VAS difference at V4, V5, V6 compared to V1 (BL) (PID V4, PID V5, PID V6) PID V4, PID V5 and PID V6 will be compared between treatment groups using ANCOVA with terms in the model for treatment group, site [as fixed effects], and baseline POM assessment [as a covariate]. Least square mean for each treatment and the corresponding difference between least square means with the p-value and 95 % confidence interval will be presented from the specified ANCOVA model.
- Sum of Pain Intensity differences (SPID) over 0-24, 0-48, 0-72 and 0-96 hours. SPID over 0-24, 0-48, 0-72 and 0-96 hours will be compared between treatment groups using ANCOVA with terms in the model for treatment group, site [as fixed effects], and baseline POM assessment [as a covariate]. Least square mean for each treatment and the corresponding difference between least square means (Active - placebo) with the p-value and 95 % confidence interval will be presented from the specified ANCOVA model.

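### The SAP gives two conflicting ANCOVA models for POM and PAR, and leaves the randomisation stratum for injury type out of the PID, SPID and log-rank analyses

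*SAP*

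**What the plan says.** Protocol sections 4 and 6.3 stratify the 1:1 randomisation by center and subgroup (sprains/strains, contusions). The analyses then treat subgroup as follows.

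- **Primary variable (SAP 14.4.1), subgroup in:** "For the primary variable an analysis-of-covariance (ANCOVA) with baseline as covariate and treatment, center and subgroup as factors will be carried out".
- **POM at every visit (SAP 14.4.2), subgroup in:** an "analysis-of-covariance (ANCOVA) model and center and subgroup as main effects". The next sentence extends this model to all other continuous outcomes, which takes in PAR.
- **POM and PAR again (SAP 14.4.2, later in the section), subgroup out:** an "analysis-on-covariance (ANCOVA) model including treatment group and center as main effects, and the baseline value as covariate".
- **PID and SPID (SAP 5.1.2 and 14.4.3), subgroup out:** "terms in the model for treatment group, site [as fixed effects], and baseline POM assessment [as a covariate". PID is defined as "POM on VAS difference at V4, V5, V6 compared to V1 (BL) (PID V4, PID V5, PID V6".
- **Time to event (SAP 14.4.2), subgroup out:** "Differences between treatments in time-to-event outcomes will be tested with the log-rank test stratified by center".
- **Ordinal outcomes (SAP 14.4.2), subgroup in:** "Differences between treatments on ordinal outcomes will be tested with Wilcoxon, stratified by center and subgroup". The responder test in the same section also uses both factors.

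Protocol 9.7.2 contains the same two ANCOVA texts and leaves the detail to the SAP, which repeats both. On the status of the secondary tests the SAP says "Statistical test results for secondary variables will only be interpreted exploratorily".

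**The concern.** A programmer cannot follow both POM/PAR texts, so these outcomes have no single prespecified model. Exploratory status limits how the results are interpreted. It does not say which model to run.

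The ambiguity reaches the primary quantity. PID V5 is POM at 72 hours against baseline, which is the primary variable. Its LS-mean difference, p-value and confidence interval are to come from a model without subgroup, while 14.4.1 requires subgroup. POM at 72 hours is also a listed secondary variable. With baseline as covariate, the raw score and the change score give the same treatment contrast, so the later POM/PAR text opens another subgroup-free route to the same result. Nothing says which result governs in the report.

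There is also an efficiency question. Where randomisation is balanced within a stratum that predicts outcome, leaving that stratum out of the model puts its variance into the residual. The standard error is then overstated and the test is conservative.

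**Working it through.** **Inputs from the documents.** SD 20 mm, difference 10 mm, two-sided 5%, 90 evaluable per group (SAP 6); 3 sites (SAP 2); strata center and subgroup (protocol 4).

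**Assumptions.** The documents give no outcome difference D between injury types, so D is shown as a range. Also assumed: within-subgroup SD 20 mm, a 50:50 split (p = 0.5) and arms balanced within strata.

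**Step 1: the plan's own figure.** Power = Φ(10 / (SD·√(2/n)) − 1.96). At n = 64, 20·√(2/64) = 3.536 and 10/3.536 − 1.96 = 0.868, which gives 80.7% (80.1% by noncentral t). Dropout: 90/0.9 = 100 per group, 200 in total. Both agree with the SAP.

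**Step 2: standard error without subgroup.** Residual variance becomes 400 + p(1−p)D², so the SE ratio is √(1 + p(1−p)D²/400).

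- D = 5: √(1 + 0.25·25/400) = 1.008
- D = 10: √(1 + 0.25·100/400) = 1.031
- D = 15: √(1 + 0.25·225/400) = 1.068

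At D = 15 a 70:30 split gives √(1 + 0.21·225/400) = 1.057. If 20 mm is instead the total SD, the ratio is 20/√(400 − 56.25) = 1.079.

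**Step 3: power and type I error, by simulation.** 20,000 trials per setting, 3 centers × 2 subgroups × 15 per arm per cell, baseline covariate in both models, treatment effect 10 mm for power and 0 for type I error.

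| D (mm) | SE ratio | Power without subgroup | Type I error without subgroup | Verdicts disagree (10 mm effect) |
|---|---|---|---|---|
| 0 | 1.000 | 91.6% | about 5% | 0.1% |
| 5 | 1.008 | 91.4% | 4.9% | 0.3% |
| 10 | 1.031 | 90.5% | 4.3% | 1.1% |
| 15 | 1.070 | 89.4% | 3.8% | 2.3% |

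With subgroup in the model, power is about 91.6% throughout. The two point estimates differ by less than 0.1 mm on average. Monte Carlo error is about 0.2 points for power and 0.15 for type I error. Putting the larger SE into the Step 1 formula at n = 90 gives 91.8/91.4/90.2/88.1%. At 10 and 15 mm this overstates the loss, because under stratified randomisation the true variance of the estimate hardly changes. Only its reported SE grows.

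**Step 4: log-rank test.** Assumed: exponential times read at the scheduled visits, placebo median 96 h, treatment hazard ratio 1.6; 20,000 trials per setting.

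| Injury-type HR | Power, center only | Power, center and subgroup | Type I error, center only |
|---|---|---|---|
| 1 | 78.2% | 77.7% | 5.0% |
| 1.5 | 76.5% | 77.4% | 5.0% |
| 2 | 73.5% | 77.4% | 4.2% |
| 3 | 65.0% | 75.4% | 3.0% |

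Type I error with both strata was 5.1–5.4%. The power levels depend on where the 96 h median sits. These figures match a median midway between the subgroups. If it belongs to the slower subgroup, the HR 3 row becomes about 69% against 81%.

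**The case against.** The strongest case against is that nothing confirmatory is touched. SAP 14.4.1 states the primary model in full, secondary tests are declared exploratory, and PID and SPID are listed as additional exploratory variables in a proof-of-concept trial. All of that stands, and it limits the weight of the point.

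The losses also rest on assumed injury-type effects. At 5 mm the power loss is 0.2 points, and the one large figure needs a hazard ratio of 3. This stands as well.

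The log-rank test is not a contradiction: the protocol and SAP agree on center only, and that test is valid. This too is correct. Adding subgroup there is an improvement in line with the randomisation, not the repair of an error. Likewise, PID and SPID each have one stated model; only the general sentence on other continuous outcomes competes with it.

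Finally, the two POM/PAR texts might be read as shorthand to be combined. The first names neither treatment nor, directly, baseline, and the second sits in a paragraph about the treatment-by-center interaction. That reading is possible but the SAP does not state it, and the second text lists its terms without subgroup. The SAP was where the protocol said this would be settled.

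**Conclusion.** The concern holds. The conflict within SAP 14.4.2 and the second, differently modelled 72-hour POM result can be seen from the text and need no assumption. The statistical cost is conditional and modest. For the ANCOVA it is none if injury type is not prognostic, about 1 power point at a 10 mm difference and about 2 points at 15 mm (91.6% to 89.4%). For the log-rank test it is about 1 point at an injury-type HR of 1.5, 4 at HR 2 and 10 at HR 3, under the assumed event-time model. The direction is conservative: negligible change in the estimate and no inflation of type I error. The primary test in 14.4.1 is unaffected. What is at stake is a clear prespecified model and one consistent result for the 72-hour change. This should be corrected, but it does not threaten the trial's main conclusion.

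**What to change.** - In SAP 14.4.2, 14.4.3 and 5.1.2, specify one ANCOVA for POM, PAR, PID and SPID: treatment, center, subgroup and the relevant baseline (PAR for PAR, POM for the rest). Delete the competing text.
- Stratify the log-rank tests by center and subgroup.
- State that 14.4.1 governs the 72-hour POM change and that PID V5 is reported from it. With one model, the secondary 72-hour POM contrast then matches it as well.
- Make the edit before unblinding. SAP section 1 already plans to finalise the document after the blind review meeting.

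The cost is SAP wording and one extra factor or stratum in the code, with no new data and no change in sample size. The ANCOVA loses one degree of freedom. If injury type is not prognostic, the log-rank test loses about 0.5 power points (78.2% to 77.7%).
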